### 10.A.3. Power for Aim 1 Analyses

A power analysis estimated the minimum detectable standardized effect (MDSE) for  $\gamma_{11}$  in the H1.1 model under a range of assumptions about the number of SBP values from each eligible patient and the intraclass correlation (ICC) in SBP values due to patients’ receiving care at the same clinics. We used data from patients (age 18-85, diagnosed with hypertension, current visit BP  $\geq 150/95$ , most recent previous encounter BP  $\geq 150/95$ ,  $\geq 1$  follow-up visit) seen 5/1/2017 through 2/28/2018 in the randomized Hyperlink clinics to inform power analysis assumptions. These patients (N=4967) had M=3.3 SBP over 10 months (Median=3, range 1-23), index  $M_{SBP}=159.9$ , index  $SD_{SBP}=16.1$ , all BP  $M_{SBP}=150.7$ , all BP  $SD_{SBP}=20.4$ , and a 3-level variance components model of SBP estimated  $ICC_{clin}=.003$  and  $ICC_{pt}=.28$ . For power estimates, conservatively assumed n=100 eligible patients in each of 20 clinics, 3 SBP per patient over 24 months and  $ICC_{clin}=.01-.03$  in a 2-level variance components model.

Under these assumptions, the H1.1 analysis is powered (80%,  $\alpha_2=.05$ ) to detect  $\gamma_{11} < -.124$  (when  $ICC_{clin} = .01$ ) and  $\gamma_{11} < -.174$  (when  $ICC_{clin}=.03$ ) so that an annual reduction in SBP that is  $20.4 * (.124-.174)=2.53-3.55$  mm Hg greater among patients in telehealth relative to clinic-based care clinics will be statistically detectable. Based on our previous research and systematic reviews, we believe a 5 mm Hg greater reduction in SBP will be achieved in eligible patients in telehealth care compared with clinic-based care. We assert that 5 mm Hg is a clinically important reduction in BP that substantially lowers the risk of stroke and heart disease, and even smaller reductions of 2 or 3 mm Hg have clinically important effects. The analysis should be sufficiently powered to observe clinically meaningful between-group differences in SBP reduction.

Patient-reported outcomes from the eligibility and 6 month surveys, corresponding to the beginning and end of intensive intervention, will be analyzed using the H1.2 model. We conservatively estimate 60% and 75% eligibility and 6 months response rates. Relative to the biologically based SBP, we anticipate higher clinic-based variance components for PROs (eg,  $ICC_{clin}=0.02-.03$ ) for PROs. The MDSE comparing 6-month PROs among telehealth relative to clinic-based care patients are  $\gamma_{11}=.239-.270$ . We expect to be able to detect 6-month differences of about 4.5 to 6 points (scale range = 0-100) on the TQSM (subscale SDs=18.7-22.6) and about 0.25 points (scale range = 1-5; SD=1.0) on the PACIC. For self-reported outcomes, a between-groups difference of Cohen’s d = .20-.30 is small, consistent with the goal of detecting meaningful differences in patient-reported side effects, care experiences, and self-management.

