## **3. Study Design**

The study compares two alternative health care service designs emerging as the dominant choices for clinicians and health systems wanting to redesign and improve hypertension care outcomes. It builds on previous hypertension quality improvement initiatives and the Hyperlink study, which used telemonitoring and telephone communication between patients and clinical pharmacists. The study design incorporates many elements of pragmatic trials: few exclusion

criteria, flexible interventions delivered in routine care, and routine follow up to determine outcomes. It is a cluster-randomized comparative effectiveness trial in 20 primary care clinics (Figure 1). [Note that 21 primary care clinics were eligible to participate (see section 4.B.) and agreed to be randomized. Four of the clinics were co-located in two buildings (two practices in each) and had shared nursing leadership. Each of the co-located clinics were randomized as one unit; therefore there are 19 units of randomization. For simplicity throughout the rest of this protocol we will continue to refer to the study as including 20 primary care clinics.] The clinic-based care approach will use recommended best practices in ~10 clinics and ~1000 patients. It relies primarily on the physician-medical assistant dyad and face-to-face visits. The telehealth care approach adapts and implements a successful research-tested model in ~10 clinics and ~1000 patients. It differs from clinic-based care through the systematic use of home BP telemonitoring and home-based telehealth care coordinated by a pharmacist. Aim 1 compares outcomes that are important to patients and other stakeholders, including BP lowering, treatment side effects, patient experience, and self-care. Aim 2 evaluates the extent and between-clinic variability of the adoption, implementation, maintenance, and reach of the interventions. Data collected for Aim 2 will also be used to monitor and improve fidelity to the interventions. Please see Appendix F for a high level overview of the study design.

To ensure that the study addresses the relevant questions and concerns of patients, caregivers, clinicians, and other healthcare stakeholders, the research team includes two patient investigators, a patient advisory board (PAB), and a stakeholder advisory board. The roles, structure and function of these individuals and groups are described more fully in section 13 (Organization) and Appendix I.

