## **10. Analysis**

## 10.A Aim 1 Primary and Secondary Analyses

The Aim 1 hypotheses pertain to the effectiveness of telehealth care, predicting that, relative to clinic-based care, it will improve SBP by a practically meaningful 5 mm Hg after 12 months of follow up (H1.1) and patient-reported outcomes (PRO) after 6 months of follow up (H1.2). H1.1 will be tested using random coefficients models in which post-enrollment SBP values will be predicted from clinic-randomized treatment group (Telehealth), time elapsed from enrollment to the SBP (YEARS), and the treatment by time interaction. The most basic form of the H1.1 model will be:

$$SBP_{ij} = \gamma_{00} + \gamma_{10} \text{Telehealth}_i + \gamma_{01} \text{YEARS}_j + \gamma_{11} \text{Telehealth}_i * \text{YEARS}_j + [u_{i0} + e_{ij}],$$

where EHR-derived SBP values documented at all qualifying encounters for 24 months will vary randomly across randomized clinics ( $u_{i0}$ ) and time ( $e_{ij}$ ). Enrolled patients will be assigned to the treatment group to which their clinic is randomly assigned, regardless of their adherence to any component of the clinic-based care or telehealth care approaches. YEARS will be scaled so that 0 represents the date of the primary care encounter at which the patient was enrolled in the study and 1 represents 365 days later. Parameter  $\gamma_{01}$  will therefore estimate the annual rate of change in SBP among clinic-based care patients, and parameter  $\gamma_{11}$  will estimate the difference in rate of SBP change among telehealth relative to clinic-based care patients. The H1.1 model will be adapted for H1.2 by replacing the YEARS component of  $\gamma_{01}$  and  $\gamma_{11}$  with a dummy indicator (6M) for whether the PRO is an enrollment or 6-month survey response.

SBP and PRO are expected to be approximately normally distributed, although the suitability of alternate error distributions and link functions will be assessed if their distributions depart from expectations. Should we observe an imbalance between study groups in the characteristics of randomized clinics, particularly in factors that moderate the fidelity with which the care models may be implemented, we may include clinic-level variables (e.g., % patients >65) as covariates or treatment modifiers, as appropriate.

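### The SBP detectable effects in 10.A.3 charge clinic-level variance to the arm-by-time contrast but use a normal multiplier; on that same basis with 17 or 18 df, power at the stated effects is about 75%, not 80%

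*Combined protocol and SAP*

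**What the plan says.** All references are to the combined protocol and SAP.

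- **10.A.3, SBP.** The calculation takes "n=100 eligible patients in each of 20 clinics, 3 SBP per patient over 24 months" and a clinic ICC of .01 to .03. The result is introduced by "Under these assumptions, the H1.1 analysis is powered (80", and the parenthesis is completed as 80% at two-sided .05. The standardized effects are .124 (ICC .01) and .174 (ICC .03), converted as "20.4 * (.124-.174)=2.53-3.55" mm Hg.
- **10.A.3, patient-reported outcomes (PROs).** The inputs are "We conservatively estimate 60% and 75% eligibility and 6 months response rates" and "ICC_{clin}=0.02-.03". The stated detectable effects are .239 to .270 SD, and for the TSQM the text adds "We expect to be able to detect 6-month differences of about 4.5 to 6 points".
- **3, Study Design.** Co-located practices were randomized together, and "therefore there are 19 units of randomization". The text then goes on referring to 20 clinics.
- **10.A.** The tested parameter is the Telehealth by YEARS interaction. On the time scale, "YEARS will be scaled so that 0 represents the date of the primary care encounter" of enrollment, and 1 is 365 days later. The basic model has one clinic term, a random intercept, plus a residual.
- **10.A.1.** Clinic-specific rates of change appear as an optional adaptation.
- **10.A.4.** Estimation is by maximum likelihood. No degrees-of-freedom method is named anywhere, and 10.A.3 does not name the reference distribution used for power.

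**The concern.** Arm is assigned by clinic. A power calculation that inflates the variance of the arm-by-time contrast by a clinic ICC treats between-clinic variation as error for that contrast. That variation has to be estimated from 19 or 20 units, and a normal critical value takes it as known. With so few units the difference is visible: the two-sided .05 critical value is 2.101 on 18 df and 2.110 on 17 df, against 1.960.

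At stake is whether the stated pair (80% power and alpha .05) holds at the stated effects. The detectable range carries some of the plan's argument: 10.A.3 says that reductions of 2 or 3 mm Hg also matter clinically, and for the PROs it gives no hypothesised effect apart from the detectable one.

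**Working it through.** **Inputs.** From 10.A.3: 10 clinics per arm (half of 20), 100 patients per clinic, 3 readings per patient, clinic ICC .01 or .03, SD 20.4 mm Hg, 80% power, two-sided .05. Assumption: readings at 0, 1 and 2 years, which gives a sum of squared time deviations of 2. The documents give the count and the span but not the spacing.

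**Step 1: reproduce the SBP figures.** Normal multiplier: 1.960 + 0.842 = 2.802.

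SE = sqrt[2(1 − ICC)(1 + 99·ICC)/(1000·2)] = sqrt[.001(1 − ICC)(1 + 99·ICC)]

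- ICC .01: SE = sqrt(.001 × .99 × 1.99) = .04439; × 2.802 = .1244 (stated .124)
- ICC .03: SE = sqrt(.001 × .97 × 3.97) = .06206; × 2.802 = .1739 (stated .174)

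None of the variants tried with 17 to 19 df came within 3% of the stated SBP values.

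**Step 2: same SEs, t reference.** The noncentrality at the stated effects is .124/.04439 = 2.794 and .174/.06206 = 2.804.

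| | 18 df (20 clinics) | 17 df (19 units) |
|---|---|---|
| Critical value | 2.101 | 2.110 |
| Power at .124 (ICC .01) | 75.2% | 75.0% |
| Power at .174 (ICC .03) | 75.6% | 75.3% |
| Multiplier for 80% power | 2.963 | 2.973 |
| Ratio to 2.802 | 1.057 | 1.061 |
| 80%-power effect, ICC .01 | .1315 SD = 2.68 mm Hg | .1320 SD = 2.69 mm Hg |
| 80%-power effect, ICC .03 | .1839 SD = 3.75 mm Hg | .1845 SD = 3.76 mm Hg |

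Section 15 (1.2) describes one vanguard stratum plus 2 to 4 others. If 3 to 5 strata were fitted with 19 units, df would be 15 to 13, and power at a noncentrality of 2.80 would be 74.5% to 73.6%. The basic H1.1 model contains no stratum terms.

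**Step 3: the normal cut-off.** If the statistic follows t on 18 df, P(|t| > 1.96) = .066. Keeping 1.96 preserves 80% power but gives a type I error of roughly 6.5%.

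**Step 4: the basic model as written.** With only a clinic random intercept, the clinic term cancels from the slope contrast, so SE = sqrt[.001(1 − ICC)].

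- ICC .01: SE = .03146; .124/.03146 = 3.94; power about 97.6%
- ICC .03: SE = .03114; .174/.03114 = 5.59; power above 99.9%

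Simulating this model with cut-off 1.96 gave type I error of .044 and .056. The results of Steps 2 and 3 do not arise here.

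**Step 5: the hypothesised 5 mm Hg.** 5/20.4 = .245 SD. With the Step 1 SEs and 17 or 18 df, power is about 96% (ICC .03) and above 99.9% (ICC .01).

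**Step 6: PROs.** With 60 respondents per clinic (60% of 100), SE = sqrt[(2/600)(1 + 59·ICC)].

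- ICC .02: SE = .08524; × 2.802 = .2388 (stated .239); × 2.963 = .253
- ICC .03: SE = .09609; × 2.802 = .2692 (stated .270); × 2.963 = .285

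On 18 df the TSQM range would be .253 × 18.7 = 4.7 to .285 × 22.6 = 6.4 points. A second reconstruction fits as closely: 75 respondents per clinic, a (1 − ICC) factor and t on 18 df give .2385 and .2704. Neither version uses both stated response rates.

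**The case against.** The strongest reply is that the plan's own primary model does not test the slope against between-clinic variation. Step 4 bears this out: for the 10.A model as literally fitted, the clinic design effect in 10.A.3 is extra caution, and a reader should not infer that the trial's true power is 75% or that its false-positive rate is about 6.5%. This objection stands and makes the point conditional. It does not rescue the power statement on its own terms, because 10.A.3 charges clinic variance to the slope and then treats it as known. If clinic slopes vary, which 10.A.1 allows for, 17 or 18 df apply.

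Second, a reader might infer that the PRO figures carry the same fault. The documents do not establish that, since the t-based reconstruction in Step 6 fits equally well.

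Third, the practical effect is small. The 5 mm Hg hypothesis keeps ample power. The assumed ICCs of .01 to .03 exceed the .003 that 10.A.3 reports from clinic data; at .003, t on 18 df gives sqrt(.001 × .997 × 1.297) × 2.963 × 20.4 = 2.17 mm Hg, better than the stated 2.53. Even .253 to .285 stays inside the .20 to .30 band that 10.A.3 treats as small for PROs. All of this stands and limits the weight of the point.

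Finally, the reference distribution is a choice of method. The SBP arithmetic is right for normal quantiles, and their use is inferred from the match rather than stated.

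**Conclusion.** The point holds in conditional form. With clinic-level variance charged to the arm-by-time contrast, as in 10.A.3, power at the stated SBP effects is about 75%, and the 80%-power effects are about 6% larger than stated. This rests on the inferred reading times, the inferred normal multiplier (strongly supported for SBP by the three-digit match) and slopes that vary between clinics. For the PROs, the stated range is consistent with the same multiplier, but the reconstruction is not unique, so no firm correction can be given from the documents. The concern does not threaten the trial's ability to detect the hypothesised 5 mm Hg and gives no reason to change its size.

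**What to change.** In 10.A.3:

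1. Recompute the H1.1 detectable effects with the noncentral t on one stated df (randomized units minus 2, less any stratum terms fitted), and restate them. With other inputs unchanged, that is 2.68 to 3.75 mm Hg on 18 df or 2.69 to 3.76 mm Hg on 17 df; the two should not be mixed in one range. Alternatively, keep the present effects and state power of about 75%.
2. Recompute the H1.2 effects the same way from the inputs actually used, stating the number of respondents per clinic.
3. Say that the calculation allows for clinic-level variation in slopes, which the basic model in 10.A does not contain, so that the reader can see which model the power refers to.

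Cost: a few sentences of rewording. The stated SBP detectable effects become about 6% less favourable; the PRO change depends on the inputs used. No change in patients or clinics.

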#### 10.A.4 Missing data

Rich pre-enrollment EHR data will enable a detailed assessment of the demographic and clinical characteristics of patients who engage in each component of the clinic-based and telehealth care approaches. While the specific reasons for engagement, or lack of engagement, are not captured, it will be possible to quantify the likelihood of engagement for well-defined segments of the eligible population. Among enrolled patients, the absence of documentation of a care process or vital sign in the EHR should not be interpreted as a missing value, but rather as indicative of a care process or test not having been performed within the health system. Truly missing observations (e.g., SBP measured, value not available) will be extremely rare, undetectable, and assumed to be missing at random (MAR). EHR derived data fields will be treated as complete for these reasons.

The HealthPartners Survey Research Center will employ state-of-the-art methods to minimize unit and item nonresponse for patient-reported outcomes. The disposition of each contact attempt to complete a survey will be documented by the Survey Research Center. For mailings and email, this includes undeliverable addresses and active refusals or volunteered ineligibility due to language that are returned via these modes. For telephone surveys, these dispositions include noncontact, refusal, ineligibility, and bad telephone number. For item nonresponse, we expect less than 5% missing data on any single item. We will use a fully conditional specification approach to build a multiply imputed H1.2 dataset that assumes unobserved values resulting from item-non-response are MAR. The imputation model will include all predictors from the H1.2 analytic model as well as EHR-derived auxiliary predictors that may be correlated with PROs to improve imputation precision.

The H1.1 and H1.2 analytic models rely on maximum likelihood approaches to estimate all parameters. These models are sufficiently flexible to accommodate unbalanced data (e.g., outcomes per patient, patients per clinic) and rely on covariance structures for model estimation so that all available data from the intent-to-treat sample contribute to parameter estimation. Mixed models are predicated on a MAR assumption which is all but certain to be met in the case of H1.1, and possibly met in the imputed H1.2 dataset.

Non-random processes such as dislike, subpar implementation, or feelings of pressure to report favorably on a care approach model may result in missing PROs, and may differentially operate across study groups. We will thoroughly examine all available EHR and survey data fields for relationships with the likelihood of missingness and values of available data. These data fields will be included in a series of multiple imputation models that add sensitivity parameters that quantify increasingly severe departures from randomness to the imputed values. We will quantify the impact of these hypothetical departures on the conclusions drawn from the MNAR imputed datasets and assess the plausibility of MNAR processes that would undermine conclusions drawn from assumed-MAR data.

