## **8.B. Patient Survey for patient-reported outcomes**

All study-enrolled patients (n=2000) will be invited to complete a series of surveys that will be the source of the patient-reported primary outcomes (i.e., treatment side effects, experiences and satisfaction with hypertension care, self-management support, confidence in self-care). Appendix H Figure 1 describes the process for collecting survey data from patients. The EHR tool will identify patients at the visit when they are enrolled in the study and transmit their contact information to the HealthPartners Survey Research Center (SRC). The SRC will mail a letter to request their participation in a series of surveys, a paper questionnaire and a \$2 non-contingent incentive, a practice known to increase response rates and reduce the likelihood of non-response error. The SRC's professional phone interviewers will call patients who do not return the paper survey to attempt to complete a survey via phone within 2 weeks of enrollment. At the end of the survey, respondents will be asked what mode they prefer for follow-up surveys 6, 12 and 24 months later. First contact for follow-up surveys will be made via the respondent's preferred mode. Non-respondents to the enrollment survey will not receive further surveys. All four surveys (enrollment, 6, 12, and 24 months) will include the patient reported outcome measures. The secondary analyses (H1.2) will make use of data collected from the enrollment and 6m surveys while other outcome analyses will make use of data collected at all four time points. Patients who complete enrollment, 6, 12, and 24 month surveys will be mailed a \$10 gift card. Patients who are on the HealthPartners Institute Exclusion List will not receive a survey.

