self-reports of these outcomes from patient surveys. Similar to the clinical effectiveness analyses, patient reported outcomes (PROs) will be collected at enrollment and then 6, 12 and 24 months later but the contrast of interest is the enrollment to 6 month change among telehealth care relative to clinic-based care patients. Missing values resulting from non-consent, non-response, loss to follow-up and item non-response increase the likelihood of misestimating PRO models. The patient survey sampling frame will include a wealth of demographic and clinical information so that we can identify characteristics that are associated with each source of missingness and develop a plan for handling missing data (e.g., multiple imputation).

4.3 Equity of patient benefit. The clinic-based care and telehealth care intervention have both been shown effective in improving hypertension outcomes. The purpose of this work is to estimate their relative effectiveness in improving clinical and patient reported outcomes. It is not expected that either of these approaches will be sufficiently superior to the other to warrant developing stopping rules for clinical benefit. Similarly, the anticipated effect sizes are sufficiently modest and accrue over a time frame such that stopping the trial early for futility would more likely result in a Type II error than offer patients a more beneficial alternative treatment.

4.4 Safety outcomes monitoring. Both interventions have been implemented in primary care settings or systematically studied with no evidence of increased likelihood of risk to patients. It is possible nonetheless that incident diagnoses related to hypertension and antihypertensive medications (e.g., hypotension / fainting, electrolyte disturbances, renal failure) and changes in lab measures indicative of antihypertensive medication (e.g., Na, K, eGFR) may be more evident among patients in one of these two treatment groups, or among patients who are exposed to the intervention as intended. The electronic health record will document each of these safety outcomes as they occur over the course of the study. Because these are more likely to be documented in outpatient than inpatient settings the lag between occurrence and documentation will be minimal.

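### In the main H1.2 analysis, EHR predictors help only with skipped items; missing 6-month surveys (25% of enrollment-survey responders) are left to a mixed model written without them

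*Combined protocol and SAP*

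**What the plan says.** **Scope of the imputation.** Section 10.A.4 describes a fully conditional specification model giving a "multiply imputed H1.2 dataset that assumes unobserved values resulting from item-non-response are MAR". The expected amount is small: "For item nonresponse, we expect less than 5% missing data on any single item". The imputation model holds the H1.2 predictors "as well as EHR-derived auxiliary predictors that may be correlated with PROs to improve imputation precision". For unit non-response, the same section describes survey methods to limit it and records of each contact attempt, but no imputation.

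**Expected response.** Section 8.B: "All study-enrolled patients (n=2000) will be invited to complete a series of surveys". Section 10.A.3: "We conservatively estimate 60% and 75% eligibility and 6 months response rates". Section 8.B adds: "Non-respondents to the enrollment survey will not receive further surveys".

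**Main model.** Section 10.A writes the basic model with arm, time, their interaction, a clinic effect and a residual. H1.2 replaces time with an indicator "for whether the PRO is an enrollment or 6-month survey response". Section 10.A.4 says the models are fitted by maximum likelihood to all available data under MAR, and regards MAR as only possibly met for H1.2.

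**Sensitivity analysis.** The last paragraph of Section 10.A.4 accepts that missing PROs may arise from non-random causes, such as dislike of the care model or poor implementation, and that these may act differently in the two groups. It plans imputations that use EHR and survey fields related to missingness and add increasingly severe departures from randomness.

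**Monitoring plan.** Section 15, item 4.2: "Missing values resulting from non-consent, non-response, loss to follow-up and item non-response increase the likelihood of misestimating PRO models". It says the sampling frame will allow the characteristics linked to each source to be identified and a plan developed, with multiple imputation as an example.

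**The concern.** The auxiliary information is aimed at the smaller loss. A skipped item on a returned survey is imputed with the help of EHR data. A whole 6-month survey that never came back is not, in the main analysis, although visits, blood pressures and medications are recorded for that patient as well.

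The mixed model does not obviously make up for this. As written it has no patient-level term, so a responder's enrollment score carries no information about that same patient's missing 6-month score. If drop-out depends on the enrollment score, or on engagement visible in the EHR, and does so differently by arm, the arm-by-wave contrast can be biased even though the data would be MAR given information already held.

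What is at stake is the H1.2 contrast for every secondary patient-reported outcome: side effects, experience of care, self-monitoring and confidence in self-care. The primary SBP outcome is not affected.

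**Working it through.** **Inputs.** 2,000 enrolled and invited (8.B); response 60% and 75% (10.A.3); only enrollment responders are surveyed again (8.B); item non-response below 5% (10.A.4); 20 clinics and clinic ICC 0.02 to 0.03 for PROs (10.A.3). Power of 80% and two-sided alpha of 0.05 are stated for H1.1 and assumed here to carry over to H1.2.

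**1. The plan's own figure.** The one computed figure that rests on the response rates is the H1.2 minimum detectable effect, 0.239 to 0.270 SD. With 10 clinics per arm and m responders per clinic,

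MDSE = (1.960 + 0.842) × √(2 × [1 + (m − 1) × ICC] / (10 × m)).

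| Responders | m | ICC 0.02 | ICC 0.03 |
|---|---|---|---|
| 1,200 (60%) | 60 | 0.239 | 0.269 |
| 900 (60% × 75%) | 45 | 0.256 | 0.285 |

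The stated range matches 1,200 responders, so it appears to use the 60% rate without the 75%. The plan does not print its formula, so this is a match and not proof, and it is a side observation. It does show that the 6-month loss is not visible in the power statement.

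**2. Number of missing 6-month surveys.** The 75% must apply to the enrollment responders, because nobody else is surveyed again.

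- Enrollment survey returned: 2,000 × 0.60 = 1,200
- 6-month survey returned: 1,200 × 0.75 = 900
- Enrollment survey only: 1,200 − 900 = 300, which is 25% of responders and 15% of enrolled
- No survey at any wave: 2,000 − 1,200 = 800, which is 40% of enrolled
- No 6-month PRO: 300 + 800 = 1,100, which is 55% of enrolled

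**3. Comparison with item non-response.** At the 5% ceiling, 0.05 × 900 = 45 patients per item. Among enrollment-survey responders, whole-survey loss at 6 months exceeds this by 300 / 45 = 6.7 to 1. Setting all 1,100 against 45 gives about 24 to 1, but that ratio mixes enrolled patients with survey responders. The first ratio is the fairer one.

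**4. What each group contributes to the main estimate as written.** The 800 contribute nothing. The 300 contribute an enrollment score to the enrollment mean of their arm, and nothing to the 6-month mean. With equal response and equal arms, the written model compares about 450 six-month scores per arm with 600 enrollment scores per arm, without linking them within patient.

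**5. Illustration of bias (assumed values).** Suppose non-responders at 6 months score g SD worse than responders in both arms, and 6-month non-response differs between arms by p. With no adjustment, the contrast is biased by g × p.

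- g = 0.3, p = 0.10: 0.03 SD
- g = 0.5, p = 0.15: 0.075 SD

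Against a detectable effect of about 0.25 SD this is 0.03 / 0.25 = 12% to 0.075 / 0.25 = 30%. Neither g nor p is given in the documents. The result is total bias with no adjustment, not the part that EHR data and baseline scores would remove.

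**The case against.** The case on the other side is substantial, and much of it limits the point.

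- **A reader might infer that the plan ignores EHR data for whole missing surveys.** It does not. The MNAR series in Section 10.A.4 uses EHR and survey fields and is not confined to item non-response. The gap is in the main H1.2 analysis.
- **A reader might infer that the MNAR series has no MAR base case.** The text does not show that. A series of graded departures naturally includes a zero-departure member. Whether that member covers whole missing surveys is simply not stated.
- **A reader might infer that the monitoring plan commits EHR data to every source of missingness.** Item 4.2 promises only to identify associated characteristics and develop a plan.
- **A reader might treat the full 55% as open to arm-dependent loss.** The enrollment survey is mailed within one week (7.B), with telephone completion sought within two weeks (8.B), and the default follow-up visit is at 1 to 2 weeks (5.A.2). The 40% lost at that stage are therefore lost largely before the intervention, which bears mainly on generalizability. The loss most exposed to patients' experience of their arm is the 300.
- **The written model is called a basic form.** Section 10.A.1 says patient covariates can be added, in the context of other analyses, and Section 10.A.4 speaks of covariance structures. A patient-level term is unspecified, not excluded. Such a term would link a patient's two scores but would still leave the EHR predictors out.
- **The benefit may be small.** The plan says only that EHR predictors may correlate with PROs.

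What remains is that the planned main imputation stops at skipped items, while the larger loss, which the plan itself suspects may differ by arm, is handled with less information than is available.

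**Conclusion.** The point holds for the main H1.2 estimate and no further. EHR auxiliary predictors are assigned there to a loss of under 5% per item. At the planned rates, 25% of enrollment-survey responders lack a 6-month survey and 55% of all enrolled patients lack a 6-month PRO; these reach the estimate only through a model written without patient-level terms or patient covariates. The sensitivity series and the monitoring plan show that the problem was recognized, but neither changes the main analysis.

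The counts rest on planning rates that the plan calls conservative, so actual losses may be smaller. The size of the bias that could be removed cannot be derived from the documents: 0.03 to 0.075 SD is an assumed illustration of total bias, and the removable part could be close to zero. Because H1.2 is secondary and the remedy is cheap, this is a worthwhile improvement to the method rather than a fault that invalidates the analysis.

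**What to change.** 1. In Section 10.A.4, extend the fully conditional specification model from item non-response to missing 6-month scores among enrollment-survey responders. Use baseline PROs and EHR-derived predictors, impute by arm, and include clinic in the model.
2. Name this as the zero-departure (delta = 0) case for the MNAR series. Each step of the series then changes only the missing-data assumption and not the set of predictors as well.
3. State in the MNAR paragraph that the series covers whole missing surveys, and align Section 10.A.4 with Section 15, item 4.2.
4. Treat the 800 enrollment non-responders as optional sensitivity work, by imputation or by weighting for response. With no PRO at any wave, their values would rest entirely on EHR associations of unknown strength.

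**Cost.** A little more analysis work, no new data collection, and possibly slightly wider standard errors. EHR predictors can be used only for responders whose consent covers their records. Section 14.C.1.a describes a consent question at the end of the survey, while Section 14.C.1.b treats return of the survey as agreement, so the plan should say which governs before the predictors are fixed.
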